1. PROTOCOL SUMMARY

1.1. Synopsis

Title:

Touch and Feel Evaluation of Two Foam Hand Sanitizers

Study Description:

Hand sanitizers are a standard of hygiene requirements. Hand sanitizers must be effective at reducing germ count on the hands while ideally providing emollients to moisturize the skin after use. To improve compliance with hand sanitizing protocols, hand sanitizers should provide a pleasant touch and feel experience for end users, especially for healthcare worker (HCW) users, who use these products frequently.

The goal of this study is to evaluate the user experience of two foam hand sanitizers produced by Medline and GOJO when used by HCWs.

The foam sanitizer products that will be evaluated in this study include:

- ➤ SpectrumTM Advanced Hand Sanitizer Foam (hereby referred to as the Spectrum product)
- > PURELL® Advanced Foam Hand sanitizer (hereby referred to as the Purell product)

Phase: Post-market.

Primary Objective: To establish the non-inferiority of the Spectrum product to the Purell product

by comparing the foam hand sanitizers with regard to the user touch and feel

experience and overall acceptability.

Primary Endpoint: The user touch and feel experience of the hand sanitizer products evaluated

by visual analog scale assessments (VAS) of HCWs overall satisfaction and

moisturization, and HCWs assessment of product preference.

Study Population: Number of participants, N = 45.

Inclusion criteria

Individuals who meet the following criteria will participate in this study:

 \rightarrow HCWs \geq 18 years of age.

Exclusion criteria

MED-2022-DIV60-001 18-NOV-2022 Version 3.0

Individuals who meet any of the following criteria will not be allowed to participate in this study:

- Individual has a skin condition that might result in irritation from the hand sanitizers.
- ➤ Individual has a known allergy to the ingredients in the test products.

Power Analysis Methods:

The sample size of 90 (45 for the foam cohort and 45 for a gel cohort to be evaluated in a future study) was estimated to provide 80% power at the 95% level of confidence for the proportion of HCWs preferring one product over the competing product using the "Non-Inferiority Tests for the Difference Between Two Correlated Proportions" procedure in PASS 2021 Power Analysis and Sample Size Software (2021). NCSS, LLC. Kaysville, Utah, USA, ncss.com/software/pass. The estimated non-inferiority margins were .03 to .08 with estimated proportion differences of .1, .15 and .20. This study utilizes the sample of N=45 for the foam product cohort.

Description of Sites/Facilities Enrolling Participants: Description of Study design: The study will be conducted at Northshore Hospitals.

This will be a prospective, single-blinded randomized cohort study that will be conducted over the course of one study visit. Participants will be asked to wash and dry their hands and apply a sanitizer product. The order in which the two hand sanitizer products are applied will be randomized. The participants will be instructed to apply the product topically to their hands and rub the product until the product is absorbed. After product application, the participants will complete a VAS assessment of their touch and feel experience with the product. Participants will then repeat the process with the second product. In the time between evaluating each product, participants will be asked to wash and dry their hands with soap and water and wait an additional two minutes after their hands have dried. After applying both products, the participants will complete a product preference questionnaire.

Participant Duration:

Approximately one hour.

1.1. Schedule of Activities (SOA)

Required Study Activities and Assessments	Visit 1
Verification of Eligibility	X
Participant Washes Hands and Waits Minimum 2 Minutes	X
Study Staff Times Participant for 2 Minute Waiting Period After Hand Washing	X
Application of Hand Sanitizer A	X
User Touch and Feel VAS Assessment	X
Participant Washes Hands and Waits 2 Minutes	Х
Study Staff Times Participant for 2 Minute Waiting Period After Hand Washing	X
Application of Hand Sanitizer B	X
User Touch and Feel VAS Assessment	X
Product Preference Questionnaire	X
Participant Dismissal	X
Adverse Events	X

2. INTRODUCTION

2.1. Background & Rationale

Hand sanitizers are a standard of hygiene requirements. Hand sanitizers are a standard tool frequently used in hospital settings by healthcare (HCWs) for hand disinfection. The Centers for Disease Control and Prevention (CDC) states that HCWs should use an alcohol-based hand rub, such as a hand sanitizer, or wash their hands with soap and water immediately before and after patient contact, during aseptic tasks, after contact with blood, bodily fluids, or contaminated surfaces, and immediately after glove removal. ¹ Additionally, the World Health Organization (WHO) guidelines on hand hygiene state that alcohol-based handrubs rapidly and effectively inactivate a wide array of potentially harmful microorganisms on hands. ² Hand sanitizers must be effective at reducing germ count on the hands while ideally providing emollients to moisturize the skin after use. To improve compliance with hand sanitizing protocols, hand sanitizers should provide a pleasant touch and feel experience for users, especially for healthcare worker (HCW) users.

The goal of this study is to evaluate the user touch and feel experience of two hand sanitizer foam products produced by Medline and GOJO when the products are used by HCWs.

2.2. Study Products

2.2.1. SpectrumTM Advanced Hand Sanitizer Foam

Spectrum Advanced Hand Sanitizer Foam is made with a 70% ethyl alcohol foaming formula that evaporates quickly on the hands and is effective at eliminating 99.99% of common germs harmful germs and bacteria. The formula includes added moisturizers to help reduce dry skin. The SKU number for Spectrum Advanced Hand Sanitizer Foam is HH70F1000 will be used with the X10 Medline Dispenser.

2.2.2. PURELL® Advanced Foam Hand sanitizer

The SKU number for PURELL® Advanced Foam Hand Sanitizer is GOJ190502 will be used with PURELL® LTX-12TM Dispenser SKU GOJ192004.

2.3. Risk/Benefit Profile

2.3.1.Potential Study Risks

This study entails minimal risk to the participants. All hand sanitizer products are commercially available and widely used in clinical settings. There is the possibility of minor skin irritation with the application of the hand sanitizer products; however, the magnitude of this should be no greater than what occurs through the normal use of the hand sanitizers. In addition, the study is designed such that the test products will be applied on the non-compromised skin of participants with no known skin conditions, which should impose less risk for study participants.

2.3.2.Potential Study Benefits

Direct benefit to the study participants is unlikely. However, the results from this study may better inform the user touch and feel experience of the study products among HCWs, which may translate into improved user experience and frequency of use of the study products by HCWs.

2.3.3. Assessment of Potential Risk/Benefit Profile

As this study entails minimal risk to the study participants and the results may further inform the user touch and feel experience of the study products by HCWs, the risk/benefit profile of this study is acceptable.

3. OBJECTIVES AND ENDPOINTS

OBJECTIVES	ENDPOINTS	JUSTIFICATION FOR ENDPOINT(S)
Primary		
1. To establish the non-inferiority of the Spectrum product to the Purell product by comparing the foam hand sanitizers with regard to the user touch and feel experience and overall acceptability.	1. The user touch and feel experience of the hand sanitizer products evaluated by VAS assessments of HCWs overall satisfaction and moisturization, and HCWs assessment of product preference.	To evaluate the HCW user touch and feel experience of the products and compare product preference between the foam hand sanitizer products.

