8. STATISTICAL CONSIDERATIONS

8.1. Sample Size Determination

Sample size N of 90 (45 for a foam cohort and 45 for a gel cohort to be evaluated in a future study) was estimated to provide 80% power at the 95% level of significant for the proportion of HCW preferring one gel/foam product over the competing gel/foam product using the "Non-Inferiority Tests for the Difference Between Two Correlated Proportions" procedure in PASS 2021 Power Analysis and Sample Size Software (2021). NCSS, LLC. Kaysville, Utah, USA, ncss.com/software/pass. The estimated non-inferiority margins were .03 to .08 with estimated proportion differences of .1, .15 and .20. This study will utilize the sample of N=45 for the foam cohort.

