8.4. Statistical Analysis

Descriptive and/or summary statistics will be calculated for the primary endpoints, which are the user touch and feel experience of the hand sanitizer products evaluated by visual analog scale assessments of HCWs overall satisfaction and moisturization, and HCWs assessment of product preference. Statistical analyses will be conducted in SAS® software, Version 9.4 or higher of the SAS System for Windows (Copyright © 2013 SAS Institute Inc.) or other appropriate statistical software.

All continuous variables will be summarized using the following descriptive statistics: n (non-missing sample size), mean, standard deviation, median, maximum and minimum. The frequency and percentages (based on the non-missing sample size) of observed levels will be reported for all categorical measures. In general, all data will be listed, sorted by site, treatment and subject, and when appropriate by visit number within subject. All summary tables will be structured with a column for each treatment in the order (Control, Experimental) and will be annotated with the total population size relevant to that table/treatment, including any missing observations.

All protocol deviations will be recorded and examined for potential bias in accordance with section 9.

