8.4.2 Assessment of Product Preference

A product preference questionnaire will be filled out by the participants after testing both hand sanitizer products. The proportion of participants showing preference of the sanitizer products will be compared within each cohort using McNemar Test for Two Correlated Proportions or other appropriate methods, depending on the distribution of data.

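### Three primary measures serve one non-inferiority objective, with no rule for which must succeed and no multiplicity control

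*Combined protocol and SAP*

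**What the plan says.** The primary objective in section 3 is "To establish the non-inferiority of the Spectrum product to the Purell product". One numbered endpoint stands against it, made up of three measures: "VAS assessments of HCWs overall satisfaction and moisturization, and HCWs assessment of product preference". The Synopsis gives the same set. Section 8.4 treats them as several endpoints: "Descriptive and/or summary statistics will be calculated for the primary endpoints".

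The comparisons follow in two subsections.

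- Section 8.4.1 has satisfaction and moisturization in its heading and gives summary statistics for every survey statement. Its comparison sentence, which offers ANOVA, t-tests or another suitable method, names only the satisfaction scores.
- Section 8.4.2 says that the proportions preferring each product "will be compared within each cohort using McNemar Test for Two Correlated Proportions", or by another appropriate method.

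Error rate, power and margins appear only in the sample-size text, and only for preference. The Synopsis gives "80% power at the 95% level of confidence for the proportion of HCWs preferring one product over the competing product". Section 8.1 adds: "The estimated non-inferiority margins were .03 to .08 with estimated proportion differences of .1, .15 and .20". No margin is given for either VAS measure.

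**The concern.** With one objective and three measures, the plan has to say what pattern of results meets the objective, and it does not. Suppose Spectrum does well on satisfaction and poorly on preference. Nothing written beforehand settles whether non-inferiority has been shown, so someone would have to choose a reading after seeing the results.

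Each reading has a price. If any one measure is enough, the chance of a false claim exceeds the level of a single test. If all are needed, the stated 80% power belongs to one component and the chance of overall success is unknown. The study's purpose is a comparative claim against a competitor's product, so the rule for that claim is the part that most needs fixing in advance.

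**Working it through.** **The plan's own figure.** Section 8.1 states "This study will utilize the sample of N=45 for the foam cohort" and 80% power for preference. The usual normal approximation for paired proportions is

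n = (z_α + z_power)² × (p_disc − d²) / (d + m)²,

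where d is the assumed difference (taken as favouring Spectrum), m the margin and p_disc the proportion of discordant pairs. The documents do not give p_disc, so I solved for the value at which n = 45 yields 80% power:

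p_disc = 45(d + m)² / (z_α + z_power)² + d².

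- One-sided 5%, (1.645 + 0.842)² ≈ 6.18. With m = .03 and d = .10, p_disc = 45 × .0169/6.18 + .01 = .133. With m = .08 and d = .20, p_disc = 45 × .0784/6.18 + .04 = .611.
- One-sided 2.5%, (1.960 + 0.842)² ≈ 7.85. The same two cases give .107 and .489.

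The 45 can therefore be neither confirmed nor refuted. In any case it concerns preference alone.

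**If any one measure sufficed.** Assume a valid test at level α on each of three measures, with non-inferiority false at the margin on all three.

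- Independent, α = .05: 1 − .95³ = .1426. Bound under any dependence: 3 × .05 = .15.
- Independent, α = .025: 1 − .975³ = .0731. Bound: 3 × .025 = .075.

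With a common correlation between the test statistics (trivariate normal; the two-sided column by simulation with 2,000,000 draws):

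| Correlation | One-sided 5% | One-sided 2.5% | Two-sided 5% |
|---|---|---|---|
| 0 | 14.3% | 7.3% | 14.3% |
| .3 | 13.0% | 6.8% | 13.6% |
| .5 | 11.8% | 6.3% | 12.5% |
| .7 | 10.3% | 5.5% | 10.9% |
| .9 | 8.0% | 4.2% | 8.4% |

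The documents state neither the side of the test nor the correlation, so both are assumptions shown as ranges.

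**If only satisfaction and preference are tested,** as the comparison sentence in 8.4.1 allows: 1 − .95² = .0975 at 5%, and 1 − .975² = .0494 at 2.5%, both under independence.

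**If all three must succeed.** Each test keeps its full α and the overall error is at most α. Joint power cannot exceed the power of the weakest component, so it is at most 80% if preference has 80%. Purely as illustration, if each measure had 80% power, the joint power would be .8³ = 51% under independence, 61% at correlation .5 and 66% at .7. The documents give no power for either VAS measure, so these are not estimates for this trial.

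**The case against.** The strongest reply is that the plan nowhere allows a claim on one measure alone. Section 3 lists one numbered endpoint whose parts are joined by a conjunction, and that can fairly be read as requiring all of them, in which case there is no inflation. This stands as a possible reading. It does not settle the matter, because section 8.4 speaks of endpoints in the plural and analyses them separately with no joint criterion.

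A reader might infer that non-inferiority can be claimed here on any one of three tested measures with an error of about 14%, whatever the other two show. The documents do not support that, for four reasons.

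- The any-one rule is not written; it is only not excluded.
- The figure presumes a valid non-inferiority test on each measure. ANOVA, the t-test and McNemar's test, as named, test for a difference. The plan gives no VAS margin and only a range of margins for preference. For the named tests, 14% is the chance of at least one false difference.
- A comparison of moisturization is suggested by the heading of 8.4.1 but not stated in its text.
- The figure takes 5% per test and independence. The level and side are not fixed for these analyses, and the same participants give all the ratings in one visit, so positive correlation is plausible.

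These points make the size conditional. They do not supply the missing success rule.

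**Conclusion.** The concern holds in conditional form. One primary non-inferiority objective rests on three measures, and the plan states no success rule, no order and no multiplicity control. The stated power covers preference only.

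If any one measure sufficed with a valid one-sided 5% test on each, the false-positive rate would be about 14% under independence and about 8% to 12% with correlations of .9 to .5, and could not exceed 15%. It would be about 7% at one-sided 2.5%, and about 9.8% at 5% with only two measures tested, both under independence. If all three were required, the error rate would be controlled, but the 80% would not describe the overall claim. The error rate of the non-inferiority claim under the plan as it stands cannot be computed, because no non-inferiority test or confidence-bound criterion is specified for the analysis of any of the three.

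**What to change.** Amend sections 3 and 8.4 before unblinding, using one of two rules.

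1. **Fixed sequence.** Test non-inferiority on preference first, at the full alpha, since the study is sized on it. Then test satisfaction and moisturization in a pre-stated order, each at the full alpha, stopping at the first failure.
2. **Single overall claim.** Require non-inferiority on all three measures, each at the full alpha. No alpha split is needed.

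Neither rule can be run without further detail, so with either one:

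- state alpha and whether tests are one- or two-sided;
- fix one margin per measure: a single value from the .03 to .08 range for preference, and a VAS margin in millimetres that the sponsor justifies;
- judge non-inferiority by comparing the paired confidence bound with that margin, keeping the difference tests as supportive at most;
- say explicitly that moisturization is tested;
- say in section 8.1 that the 80% power applies to preference only.

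The cost is a modest rewrite of these sections plus the work of justifying the VAS margins. Neither rule calls for new data collection. Under the first, the VAS claims become conditional on preference; under the second, one failure defeats the overall claim, whose power the documents do not support at any stated figure.

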4. STUDY DESIGN

4.1. Overall Design

This will be a prospective, double-blinded randomized cohort study that will be conducted over the course of one study visit. Participants will evaluate two foam hand sanitizer products.

The requirement to obtain informed consent will be waived for this clinical study. Following screening for eligibility, successfully enrolled participants will be asked to wash and dry their hands and apply one of two foam hand sanitizer products. The order in which each product is applied first will be randomized. The participants will be instructed to apply the first product (Hand Sanitizer A) topically to their hands and rub the product until the product is absorbed. The aliquot provided from the automated dispenser will be approximately 1 mL of each hand sanitizer product. After product

application, the participants will complete a VAS assessment of their touch and feel experience with Hand Sanitizer A. The participant will then be asked to wash and dry their hands with soap and water and wait an additional two minutes after their hands have dried. The participant will then repeat the described process with the second product (Hand Sanitizer B). After applying the two foam Hand Sanitizers A and B, the participant will complete a product preference questionnaire. At this point, the participant has completed the study and will be dismissed.

4.2. End of Study Definition

This study will be considered complete upon issuance of a Clinical Study Report that has been approved by the Clinical Affairs Director.

5. STUDY POPULATION

5.1. Inclusion Criteria

Individuals who meet the following criteria will participate in this study:

 \rightarrow HCWs \geq 18 years of age.

5.2. Exclusion Criteria

Individuals who meet any of the following criteria will not be allowed to participate in this study:

- > Individual has a skin condition that might result in irritation from the hand sanitizers.
- > Individual has a known allergy to the ingredients in the test products.

5.3. Strategies for Recruitment and Retention

Participants will be recruited during staff meetings at Northshore hospitals.

6. STUDY PROCEDURES AND ASSESSMENTS

6.1. Visit 1

6.1.1.Informed consent and screening

6.1.1.1. Informed Consent

The requirement to obtain informed consent from the participant will be waived for this clinical study.

MED-2022-DIV60-001 18-NOV-2022 Version 3.0

6.1.1.2. Verification and Eligibility

The PI or delegated study staff will verify the eligibility of the individual for the study, based on the inclusion and exclusion criteria that will be evaluated in the Participant Screening Form. The participant will receive a unique screening number that will be recorded in the Participant Screening Form. The participant responses will be included in the Participant Screening Form.

Successfully enrolled participants will be assigned a unique participant identification number based on the order in which they enroll. If the individual is considered eligible to participate in the study, the participant will proceed to the study activities detailed in sections 6.1.2, 6.1.3, 6.1.4, and 6.1.5.

6.1.2. Participant Cohort Randomization

Participants will be assigned to evaluate two foam hand sanitizers. The order in which the participants test a hand sanitizer product first or second will be randomly assigned. The participants, as well as on-site staff will be blinded to testing products. If a participant is unable to complete the study or has missing data, the participant will be replaced such that the new participant will be assigned to the randomization cohort of the replaced participant. Randomization schedule will be generated using SAS® software, Version 9.4 of the SAS System for Windows. Copyright © 2013 SAS Institute Inc.

6.1.3. Hand Sanitizer A Application and Touch and Feel Assessment

Study staff will be provided with hand sanitizers and dispensers to use prior to handling any items such as product bottles, pens, or paperwork, for the duration of the study activities.

Participants will first be asked to wash and dry their hands and wait an additional two minutes after their hands have dried before application of the hand sanitizer products. Study staff will use a stopwatch set for two minutes to ensure participant compliance to the two minute waiting period after hand washing. The participants will be instructed by study staff to apply one automatically dispensed amount, approximately 1 mL, of the first product (Hand Sanitizer A) topically to their hands and rub the product until the product is absorbed. The order in which each product is applied will be randomized. After product application, the participants will complete a VAS assessment of their touch and feel experience with Hand Sanitizer A, which will include questions regarding the participant's perceived moisturization and overall satisfaction with the hand sanitizer. Participant responses to the assessment will be recorded in the CRF by study staff.

6.1.4. Hand Sanitizer B Application and Touch and Feel Assessment

The participant will again be asked to wash their hands with soap and water and dry their hands and wait an additional two minutes after their hands have dried. Study staff will again time the two minute waiting period using a stopwatch. The participant will then repeat the described application process with the second product (Hand Sanitizer B), as the participants will be instructed by study staff to apply one automatically dispensed amount of approximately 1 mL of Hand Sanitizer B topically to their hands and rub the product until the product is absorbed. After product application, the participant will complete a VAS assessment of their touch and feel

experience with Hand Sanitizer B. Participant responses to the assessment will be recorded in the CRF by study staff.

